3.2. SPECIFIC AIM 2: Clinical Evaluation and Patient Experience

Patient selection and image acquisition: Fifty patients referred to the UNC Section of Oral and Maxillofacial Radiology for bitewing or full-mouth series exams will be recruited following completion of their ordered radiographic exams. Patients with moderate caries will be approached about participation in the study. Consenting patients will then receive a 4-bitewing exam using the s-IOT system. We will acquire both the ordered conventional radiographic exam and the s-IOT exam. The same group of patients will be tested for both caries detection evaluation and patient care experience.

Caries detection: Three UNC SOD dentists will be recruited to independently review each radiographic exam to diagnose caries presence/absence. Discrepancies between reviewers will be reconciled by consensus.

Verification: In vivo assessment of the true state of a proximal tooth surface is challenging. For the purpose of this study, cases where a proximal tooth surface received a caries diagnosis on the s-IOT images and not on the conventional images, or vice versa, are of particular interest. For these cases, the patient's clinician will be contacted to perform reversible mild clinical tooth separation to allow visual assessment of caries status.

Data analysis: The goal of the data analysis is to test (1) whether differences in the caries detection rate between s-IOT and conventional radiographs are present and (2), if so, whether these differences result from s-IOT being more sensitive. With 50 patients x 4 images/patient x ~4 teeth/image x 2 surfaces/tooth = 1600 surfaces, we expect sufficient statistical power to detect diagnostic differences.

A statistical test for paired nominal data, such as the McNemar's test, would be used to test the first hypothesis while accounting for within-patient and within-tooth/image correlations. Sensitivity, specificity and diagnostic accuracy are calculated from the clinically verified cases to characterize and quantify the modalities and will be compared regarding the second component of the hypothesis. To obtain proper inference to account for complex correlations within the same patient, or the same tooth, or the same image, resampling approach based on bootstrapping over 50 patients will be used to obtain correct variances for all statistics. NC TraCS statistician ([name]) will help perform the above data analysis.

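### Sensitivity, specificity and accuracy are to be computed from surfaces verified only where the two modalities disagree, so each s-IOT/conventional pair sums to 100% and does not measure device performance

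*Combined protocol and SAP*

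**What the plan says.** All the relevant text is in section 3.2 (Specific Aim 2) of the combined protocol and SAP.

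- **Reads.** "Three UNC SOD dentists will be recruited to independently review each radiographic exam to diagnose caries presence/absence". Then: "Discrepancies between reviewers will be reconciled by consensus". This gives one binary call per surface and modality.
- **Verification.** The plan concedes: "In vivo assessment of the true state of a proximal tooth surface is challenging". It singles out "cases where a proximal tooth surface received a caries diagnosis on the s-IOT images and not on the conventional images, or vice versa" and continues: "For these cases, the patient's clinician will be contacted to perform reversible mild clinical tooth separation to allow visual assessment of caries status". Verification of surfaces on which the modalities agree, or of a sample of them, is described nowhere.
- **Analysis.** Hypothesis 1 asks whether detection rates differ. Hypothesis 2 asks "whether these differences result from s-IOT being more sensitive". For the latter, "Sensitivity, specificity and diagnostic accuracy are calculated from the clinically verified cases to characterize and quantify the modalities", and the results are compared between modalities.
- **Variance.** A "resampling approach based on bootstrapping over 50 patients will be used to obtain correct variances for all statistics". No correction for partial verification is described.

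**The concern.** The surfaces that enter the performance figures are chosen because the two modalities disagree on them. Lesions found by both, lesions missed by both, and the large group of sound surfaces called sound by both all drop out. On what is left, one modality's success is by definition the other's failure. The results would look like sensitivity, specificity and accuracy and would be read as such, but they could not tell two excellent devices from two poor ones.

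At stake are the only performance estimates planned for hypothesis 2. A specificity near 50% would unfairly condemn both devices, and a depressed conventional sensitivity would flatter s-IOT. The patient bootstrap gives variances that respect clustering, but it resamples the same selected surfaces and so leaves the selection in place.

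**Working it through.** **The plan's own figure.** 50 patients × 4 images × 4 teeth × 2 surfaces = 1600 surfaces, as stated. The identity below needs no further input.

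**Identity.** Take one consensus call per modality and verification of discordant surfaces only. Among verified carious surfaces, let b be those found only by s-IOT and c those found only by conventional imaging. Among verified sound surfaces, let f be those called carious only by s-IOT and g those called carious only by conventional imaging. Let T = b + c + f + g.

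| | s-IOT | Conventional | Sum |
|---|---|---|---|
| Sensitivity | b/(b+c) | c/(b+c) | 1 |
| Specificity | g/(f+g) | f/(f+g) | 1 |
| Accuracy | (b+g)/T | (c+f)/T | 1 |

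This holds even if only some discordant surfaces are verified. In 2000 simulated data sets with incomplete verification, every pair summed to 100%. Two identical devices give 50/50 in expectation on all three measures, whether their true sensitivity is 30%, 50% or 70%.

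**Inflation of the gaps** (all discordant surfaces verified). The true sensitivity gap is (b−c)/(all carious surfaces); the reported gap is (b−c)/(b+c). The inflation factor is therefore 1/(discordant share of carious surfaces). For accuracy it is 1/(discordant share of all surfaces).

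**Illustration: inputs.** Conventional sensitivity 50% is the mid-point of the 30–70% in section 1.1. s-IOT sensitivity is 0.50 × 1.36 = 68%, reading the 36% gain in section 2.2 as relative. Assumed, because the documents do not give them: prevalence 10%, specificity 95% for both, reads independent given true status.

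| Expected surfaces | Both positive | s-IOT only | Conventional only | Neither |
|---|---|---|---|---|
| Carious (160) | 54.4 | 54.4 | 25.6 | 25.6 |
| Sound (1440) | 3.6 | 68.4 | 68.4 | 1299.6 |

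Discordant total: 54.4 + 25.6 + 68.4 + 68.4 = 216.8, or 13.6% of 1600.

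| s-IOT vs conventional | As planned | True |
|---|---|---|
| Sensitivity | 54.4/80 = 68% vs 25.6/80 = 32% | 68% vs 50% |
| Specificity | 68.4/136.8 = 50% each | 95% each |
| Accuracy | 122.8/216.8 = 56.6% vs 94.0/216.8 = 43.4% | 92.3% vs 90.5% |

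The sensitivity gap is inflated 160/80 = 2.0 times (36 points against 18). The accuracy gap is inflated 1600/216.8 = 7.4 times (13.3 points against 1.8). The match of 68% for s-IOT is a coincidence of a conventional sensitivity of exactly 50% with independent reads. With conventional at 30%, s-IOT's true 40.8% would be reported as 61.7%.

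**Ranges.**

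- Conventional 30%: sensitivity gap reported 23 points, true 11. Conventional 70%: 79 against 25.
- 36% read as percentage points (86% vs 50%): 72 against 36.
- Prevalence 5–30% and specificity 90–98%: accuracy gap reported 4.6–30.4 points, true 0.9–5.4.
- Correlation of 0.3 between reads within each disease state: sensitivity 75% vs 25%, with true performance unchanged.
- s-IOT specificity 93% against 95%: f = 95.76 and g = 66.96, so the plan reports 66.96/162.72 = 41% vs 59%.

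**What the same data can estimate.** If every discordant surface is verified correctly, concordant surfaces cancel in differences taken over all surfaces read:

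- net extra true positives: (54.4 − 25.6)/1600 = 1.8 per 100;
- net extra false positives: (68.4 − 68.4)/1600 = 0;
- accuracy difference: (122.8 − 94.0)/1600 = 1.8 per 100, which equals 92.3% − 90.5%.

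In the 93% vs 95% case they give 1.8 extra true and 28.8/1600 = 1.8 extra false positives per 100, so an accuracy difference of 0, which is again the truth.

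**Limits of those contrasts** (assumed error and verification rates).

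- If visual assessment finds 80% of carious surfaces, net true positives are 1.44, net false positives 0.36 and the accuracy difference 1.08 per 100.
- Suppose both sensitivities are 50%, specificity is 90% (s-IOT) vs 95%, and visual assessment calls 5–10% of sound surfaces carious. Then b − c is expected to be 0.05 × 72.0 = 3.6 to 0.10 × 72.0 = 7.2 instead of 0.
- If a fraction v of each direction is verified, base-case b − c lies between 28.8v − 94.0(1−v) and 28.8v + 122.8(1−v): 16.5 to 38.2 at v = 0.9, and −8.0 to 57.0 at v = 0.7.

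**The case against.** The strongest reply is that hypothesis 2 is directional and survives. Comparing b/(b+c) with c/(b+c) is a test of b = c, and equal sensitivities give 50/50 in expectation. With complete and correct verification, the planned comparison therefore has the right null, and the first part of the remedy below largely repeats it. That stands: the defect lies in the estimates and their labels, not in the null hypothesis. But the plan also undertakes to quantify the modalities, and that it cannot do.

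Three further points have some force.

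- **Verified cases might include concordant surfaces.** The text does not forbid this, but it describes no such verification.
- **The plan does not say which read triggers verification.** If one reader's disagreement were enough, some surfaces concordant at consensus would be verified and the sums need not be exactly 100%. The same applies to per-reader figures before consensus. Both would still rest on surfaces selected for disagreement.
- **This is a first patient evaluation, and verifying only discordant surfaces is a practical choice.** That is reasonable, and it is why the remedy changes the analysis and not the verification.

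**Conclusion.** The concern holds. Given one consensus call per modality and the only verification the plan describes, the 100% sums are an algebraic identity that needs no assumption about prevalence, specificity or correlation. Those assumptions set only the size of the distortion: in the illustration, a two-fold inflation of the sensitivity gap, a 7.4-fold inflation of the accuracy gap, and a specificity of 50% where the truth is 95%.

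Hypothesis 1 needs no verification and is unaffected. For hypothesis 2, the direction of a sensitivity or specificity difference can be tested, but its size cannot be estimated, because the numbers of carious and sound surfaces are unknown. Net true positives, net false positives and the accuracy difference over all surfaces read can be estimated in size. They need discordant surfaces to be fully verified, or verified independently of true status within each direction, and the visual assessment to be correct. The plan as written would report wrong performance figures, so it should be changed before analysis.

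**What to change.** Replace the sentence on sensitivity, specificity and accuracy in section 3.2 as follows.

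1. Do not report these measures from verified discordant surfaces as performance of the modalities. For hypothesis 2, compare s-IOT-only with conventional-only positives among verified carious surfaces (tests equal sensitivity) and, separately, among verified sound surfaces (tests equal specificity).
2. Report net extra true positives, net extra false positives and the accuracy difference per 100 surfaces read by both modalities, with patient-bootstrap intervals.
3. State the assumptions: visual assessment after separation classifies surfaces correctly, and verification is complete or unrelated to true status given the direction of disagreement.
4. Report verified out of discordant counts by direction. If any are unverified, weight each direction by the inverse of its verified fraction, in the tests as well as the estimates, and add worst-case bounds. For example, b = c = 40 verified at 90% and 60% gives 36 against 24 unweighted; weighting restores 36/0.9 = 24/0.6 = 40.
5. Give any absolute sensitivity or specificity only as a labelled sensitivity analysis that takes concordant reads as correct. In the illustration this yields sensitivity 112.4/138.0 = 81.4% vs 83.6/138.0 = 60.6% (true 68% vs 50%) and specificity 1393.6/1462.0 = 95.3% for both (true 95%), so the label is essential. Omitting it is also acceptable.

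The cost is analysis wording and a tally of verified and unverified discordant surfaces by direction, with no extra patients, readers or procedures. The price is giving up headline absolute accuracy figures, which this design cannot estimate anyway.

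### Accuracy is calculated only from the discordant surfaces that were verified, with no adjustment if completion differs between s-IOT-only and conventional-only surfaces

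*Combined protocol and SAP*

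**What the plan says.** All of the relevant text is in section 3.2 (Specific Aim 2).

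- **What is verified.** The surfaces of interest are "cases where a proximal tooth surface received a caries diagnosis on the s-IOT images and not on the conventional images, or vice versa". The request therefore covers both directions of disagreement. Surfaces on which the modalities agree are not sent.
- **How.** For these surfaces, "the patient's clinician will be contacted to perform reversible mild clinical tooth separation to allow visual assessment of caries status". No completion rate, deadline or fallback is given.
- **What is calculated.** "Sensitivity, specificity and diagnostic accuracy are calculated from the clinically verified cases to characterize and quantify the modalities". These figures are then compared for the second hypothesis: "2), if so, whether these differences result from s-IOT being more sensitive".
- **What is adjusted.** A "resampling approach based on bootstrapping over 50 patients will be used to obtain correct variances for all statistics". This deals with correlation within patient, tooth and image.
- **The first hypothesis** has its own analysis: "A statistical test for paired nominal data, such as the McNemar's test, would be used to test the first hypothesis".

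Section 4 (Risk and Remedy) discusses recruitment and the number of surfaces, but not incomplete verification.

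**The concern.** Verification is done by someone outside the reading study, so it may not be completed for every surface. The plan names the verified surfaces as the basis for accuracy and gives no rule for the rest. Read literally, it pools whatever comes back.

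Only discordant surfaces are verified, so each verified carious surface is a true positive for one modality and a miss for the other. The sensitivity comparison thus reduces to the number of verified carious surfaces in the s-IOT-only cell against the number in the conventional-only cell. If one cell is verified more completely than the other, that comparison shifts for a reason unrelated to the devices.

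The second hypothesis is at stake. Discordant-only verification cannot give absolute sensitivity or specificity, but with complete or balanced verification it still shows which modality finds more true lesions. Unbalanced completion undermines that remaining comparison, in either direction.

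**Working it through.** **The plan's own figure.** 50 × 4 × 4 × 2 = 1600 surfaces, as stated. The plan gives no alpha, power, effect size, discordance rate or verification rate, so there is nothing further to reproduce.

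**Notation.** Let b1 and c1 be the truly carious s-IOT-only and conventional-only surfaces, b0 and c0 the sound ones, and vb and vc the verified fractions. Among verified surfaces:

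- Sensitivity, s-IOT = vb·b1 / (vb·b1 + vc·c1). For conventional it is the complement.
- Specificity, s-IOT = vc·c0 / (vb·b0 + vc·c0). For conventional it is the complement.
- Ratio of verified true positives = (vb/vc) × (b1/c1).

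The last line is algebra and needs no assumed rates. The bootstrap resamples patients from the same verified set, so the factor vb/vc stays in the estimate.

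**Assumptions for the illustration (not in the documents).** Prevalence is 10% of surfaces, giving 160 carious and 1440 sound. Each modality has a 5% false-positive rate, and readings are conditionally independent. Conventional sensitivity is 50%, inside the 30% to 70% range in section 1.1. s-IOT sensitivity is 68%, which takes the 36% gain in section 2.2 as relative (0.50 × 1.36); the text does not say whether it is relative or absolute. The sensitivity shares below do not depend on the assumed prevalence.

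**Case A: true sensitivities 68% and 50%.** b1 = 160 × 0.68 × 0.50 = 54.4; c1 = 160 × 0.50 × 0.32 = 25.6; ratio 2.125.

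| vb / vc | Verified b1 | Verified c1 | Shares | Ratio |
|---|---|---|---|---|
| equal (100% shown) | 54.4 | 25.6 | 68/32 | 2.125 |
| 50% / 80% | 27.2 | 20.5 | 57/43 | 1.33 |
| 80% / 50% | 43.5 | 12.8 | 77/23 | 3.40 |

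Even with equal verification, 68/32 is not the true 68/50. The two figures must sum to 100 because only discordant surfaces enter.

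**Case B: equal true sensitivity of 50%.** b1 = c1 = 160 × 0.5 × 0.5 = 40. At 90%/60% the verified counts are 36 and 24, so 60/40 for identical devices. Reversing the rates gives 40/60.

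The plan names no test for this comparison. As an illustration, a two-sided 5% sign test was simulated (20,000 runs, independent surfaces). It rejects in about 5% of runs with equal verification and in 34% at 90%/60%. With b1 = c1 = 20, the figure at 90%/60% is 20%. Clustering within patients would change these rates but not the bias.

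**Case C: true sensitivities 60% and 50%.** b1 = 48 and c1 = 32. At 60%/90%, both verified counts are 28.8, so a real difference disappears.

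**Specificity.** b0 = c0 = 1440 × 0.05 × 0.95 = 68.4. At 90%/60%, s-IOT = 41.04 / (61.56 + 41.04) = 0.40 and conventional = 0.60, although the true values are equal. The shift is opposite to that in sensitivity.

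**Check of the repair, Case A at 50%/80%.** The s-IOT-only cell holds 54.4 + 68.4 = 122.8 surfaces. Of these 61.4 are verified and 27.2 found carious, so 122.8 × 27.2/61.4 = 54.4. The conventional-only cell holds 94.0. Of these 75.2 are verified and 20.48 found carious, so 94.0 × 20.48/75.2 = 25.6. The ratio of 2.125 is restored, provided that verification is unrelated to true status within a cell.

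**The case against.** The strongest reply is that the plan treats the two directions alike: every discordant surface is to be verified, by one route, whichever modality was positive. No completion rate is given, and nothing makes the request unequal. A clinician or patient who does not cooperate would probably remove that patient's surfaces in both directions, which pulls the two fractions together. The sentence on verified cases says which surfaces are used and is silent on non-completion; it does not announce a complete-case policy. This stands, and it makes unequal verification an unaddressed risk and not a feature of the design.

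Three stronger readings are tempting but unsupported.

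- A reader might infer that conventional-only surfaces will be verified more often, because the ordered exam belongs to the patient's care. But study positives come from the consensus of three recruited dentists, and the plan does not say that the treating clinician made or shared those calls. No direction of bias can be predicted.
- A reader might take the change in raw true-positive difference as the size of the bias: in Case A, 28.8 becomes 6.7 at 50%/80% and 30.7 at 80%/50%. Those figures mix imbalance with overall loss. Balanced 65% verification alone gives 28.8 × 0.65 = 18.7.
- A reader might infer that the conclusion would be reversed. In Case A, s-IOT still leads in both unequal scenarios shown. Reversal there needs vb/vc below 25.6/54.4 = 0.47.

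It can also be said that discordant-only verification is the larger limitation. That is fair for absolute accuracy. It does not dispose of this point, because the direction of the comparison survives that limitation but not unbalanced completion.

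**Conclusion.** The point holds as a conditional one. The plan requests verification symmetrically but bases accuracy on the surfaces actually verified, with no adjustment if completion differs by direction. If it does differ, the true-positive ratio is multiplied by vb/vc, specificity is distorted too, and the bootstrap corrects neither. Under the stated assumptions the distortion runs from 68/32 to 57/43 or 77/23, and it can create a 60/40 split between equally sensitive devices. The documents supply no verification rate, so these sizes show a range and are not predictions. Only the second hypothesis is exposed; the paired test of detection needs no verification. The correction is a matter of analysis only and should be specified before verification results are seen.

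**What to change.** In the data analysis part of section 3.2:

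1. For each direction of discordance, report the surfaces found, sent and verified.
2. Estimate true positives in each discordant cell as the cell total times the proportion of its verified surfaces found carious, and false positives as the cell total times the proportion found sound. Do this within each bootstrap resample of patients. State the assumption that verification is unrelated to true status within a cell.
3. Compare the modalities on these weighted discordant counts, as a difference or a ratio. Do not present them as absolute sensitivity and specificity, which discordant-only verification cannot give.
4. Add a sensitivity analysis in both directions: take the unverified surfaces in each cell in turn as all sound and all carious. In Case A at 50%/80%, the s-IOT-only count would run from 27.2 to 27.2 + 61.4 = 88.6, and the conventional-only count from 20.5 to 20.5 + 18.8 = 39.3. Such bounds are wide when completion is low, which is itself a reason to report completion by direction.

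The cost is analysis wording and a little programming, with no extra procedures. Intervals will be somewhat wider than from simple pooling, and may be unstable if a verified cell is small among 50 resampled patients.

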4. RISK AND REMEDY

Our team has considerable experience in characterizing, and certifying medical devices. We do not anticipate any risk in this aspect of the project. Prior to implementation, the Radiation Safety Committee and IRB will assess this study. There is minimal risk to participants, investigators, and study personnel. The radiation dose from the s-IOT exam is comparable to the dose from the conventional 2D bitewing exam, dictating that the additional radiation burden to the patient represents no greater than minimal risk and technically does not require review and approval by the RSC (5 or fewer dental x-rays). Given the high patient volume at the UNC SOD, we do not anticipate problems with patient availability and recruitment. The sampling, 1600 distinct teeth surfaces, is substantially larger than what we have previously used for similar studies, and should provide sufficient statistical power to detect the diagnostic differences.

